### 7.2 Exclusion criteria

- 1) Average of systolic BP  $< 110$  or  $> 160$  mm Hg at baseline
- 2) Average of diastolic BP  $> 100$  mm Hg at baseline
- 3) Type 1 DM (WHO criteria)
- 4) HbA1c  $< 6.5\%$  (48 mmol/mol) AND  $> 5$  years of known duration of diabetes type 2 AND never treated with an antidiabetic drug of any kind.

- 5) Current in treatment with more than one RAAS blocking agent (Angiotensin Converting Enzyme inhibitor, Angiotensin Receptor Blocker or Direct Renin Inhibitor)
- 6) Current lithium treatment (ATC: N05AN)
- 7) Known or suspected hypersensitivity to Spironolactone or to any of its excipients.
- 8) Current use of potassium sparing diuretics (ATC: C03D, C03E), such as: Spironolactone, Eplerenone or amiloride etc.
- 9) Hyperkalemia at Screening: Plasma potassium level >5.0 mmol/L or serum potassium level >5.4 mmol/L.
- 10) Hyponatremia determine by the investigator
- 11) Current cancer treatment or within five years from baseline (except basal cell skin cancer or squamous cell skin cancer)
- 12) Any clinically significant disorder, except for conditions associated with type 2 DM history, which in the Investigators opinion could interfere with the results of the trial
- 13) Cardiac disease defined as: Heart failure (NYHA class III-IV) and/or diagnosis of unstable angina pectoris and/or MI, stroke, PTCA or CABG within the last 3 months
- 14) Diagnosis of non-Diabetic CKD current or in the past
- 15) Diagnosis of liver cirrhosis with current impaired liver function within the last 3 years.
- 16) Diagnosis of Addison's disease.
- 17) Being lactating.
- 18) Intend to become pregnant within the duration of the study or not use adequate birth control.
- 19) Known or suspected abuse of alcohol or narcotics
- 20) Not able to understand informed consent form
- 21) Participation in any other intervention trial than PRIORITY or a related sub-study is not allowed within 30 days before inclusion or concurrent to this study

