4.3.2 Observational cohort

All participants with valid proteomic score and data at baseline visit.

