6.1.2 Secondary outcome

- A. Comparison of composite fatal and non-fatal cardiovascular outcome (MI, stroke, CABG, PTCA, hospitalization for heart failure and CVD) and all-cause mortality during the study.
- B. Comparison of incidence of retinopathy and frequency of laser treatment. Data collected from self-reported AEs.
- C. In addition to the categorical analysis of UACR, an analysis will be performed with changes in geometric mean of UACR throughout the study period in all patients by assessing the slope of albuminuria changes and absolute changes from inclusion to end of trial.
- D. Development of microalbuminuria (UACR >30 mg/g) in at least one morning void urine sample will be used as a secondary outcome instead of confirmed microalbuminuria.
- E. Development of macroalbuminuria (UACR >300 mg/g) in 2 out 3 first morning void urine samples).
- F. For patients with eGFR ≥ 60 ml/ min/ 1.73 m² at baseline, development of eGFR <60 ml/min/1.73m².
- G. Development of CKD stage 4 (eGFR <30 ml/min/1.73m²).
- H. Change in eGFR (slope) from baseline and from three-month post-baseline to end of study.
- I. Change in eGFR (40 % reduction) from baseline and from three-month post-baseline to end of study.
- J. Safety: Adverse Events and Serious Adverse Events. Adverse Events leading to death or discontinuation of study medication and/or withdrawal.
- K. Event of hyperkalaemia with potassium level in plasma ≥ 5.5 mmol and/or ≥ 5.8 mmol in serum at any time point.

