6.3.1.2 Analysis of secondary endpoints

Based on a 2x2 table included the primary endpoint (event/ event free) vs. risk stratification ("high"/- "low"-risk) we will calculate sensitivity, specificity and numbers need to screen for CKD273 and tested for significance using Chi-square test. In a logistic model we will added value using AUC and ROC with comparison between "high"- and "low"-risk vs. event and event-free for both primary endpoint. The logistic models will be performed both unadjusted and adjusted for age, gender, HbA_{1c}, systolic blood pressure, retinopathy, eGFR and UACR at baseline.

For the Cox-regression model a model, including adjustment for age, gender, Hba1c, systolic blood pressure, retinopathy eGFR and UACR at baseline will be comprised for secondary endpoints (see section 6.1.1 and 6.1.2, excluding 6.1.2 C, H and J).

For further clarification of the added value for discrimination, the rIDI will be calculated based on all above described Cox-regressions models with a significant HR for CKD273 in the unadjusted model for each endpoint.

To evaluate changes in UACR and eGFR over time (outcome measurement C and H in section 6.2.1) a linear mix model will be applied with adjustment for eGFR and UACR at baseline.

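### SAP 6.3.1.2 leaves hyperkalaemia (outcome K) in the CKD273 high- versus low-risk Cox models, where spironolactone use and denser potassium testing can both inflate the hazard ratio

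*SAP*

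**What the plan says.** SAP 6.3.1.2 (observational study) applies its adjusted Cox model to "secondary endpoints (see section 6.1.1 and 6.1.2, excluding 6.1.2 C, H and J". Outcome K is not on that exclusion list. SAP 6.1.2 defines it as "Event of hyperkalaemia with potassium level in plasma ≥ 5.5 mmol and/or ≥ 5.8 mmol in serum at any time point", so one reading is enough and no confirmation is needed. The neighbouring safety outcome J, "Safety: Adverse Events and Serious Adverse Events", is excluded.

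The determinant is the CKD273 stratum. The covariates are listed as "adjustment for age, gender, Hba1c, systolic blood pressure, retinopathy eGFR and UACR at baseline will be comprised"; neither treatment allocation nor visit frequency is among them. The SAP adds that "the rIDI will be calculated based on all above described Cox-regressions models with a significant HR for CKD273 in the unadjusted model", for each endpoint.

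SAP 4.3.2 defines the analysis set as "All participants with valid proteomic score and data at baseline visit", which takes in both randomised arms. Protocol 11.1 gives study drug to the intervention group only, and Protocol 11.3 lists hyperkalaemia among the side effects of spironolactone. Protocol 10.8 and Table 1 require potassium at every visit. For high-risk patients that means week 2, every 13 weeks and the end visit. For low-risk patients it means yearly and the end visit.

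**The concern.** The model is meant to show what the score predicts. For K, the two strata differ by design in two other respects that bear on the outcome. About half of the high-risk stratum takes a drug that can raise potassium, and no low-risk patient does. The high-risk stratum also has many more occasions on which a single high value can be caught. Neither difference is a property of the urinary peptide pattern, and the listed covariates remove neither.

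The result would be reported beside the renal and cardiovascular endpoints. A hazard ratio well above 1, followed by an rIDI, could then be read as added value of CKD273 when it reflects allocation and visit schedule.

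**Working it through.** **Plan's own figure.** The documents give no expected rate, hazard ratio or sample size for K, so there is nothing to reproduce. The figures below are assumptions shown over a range.

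**Scheduled potassium tests after baseline (Table 1).**

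| Point in follow-up | High risk | Low risk |
|---|---|---|
| By week 104, end visit not counted | 1 + 8 = 9 | 2 |
| By week 156, end visit not counted | 1 + 12 = 13 | 3 |
| 230 weeks, end visit counted | 1 + 17 + 1 = 19 | 4 + 1 = 5 |

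The leading 1 in the high-risk column is the week 2 visit.

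**Simple calculation, transient excursions.** Assume independent tests, a per-test event probability p, and no CKD273 effect. The probability of at least one event in n tests is 1 − (1 − p)^n. In the high-risk stratum, average two halves, with p multiplied by the drug's relative risk (RR) in the active half.

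- 13 v 3, p = 0.01: (1 − 0.99^13) / (1 − 0.99^3) = 0.1225 / 0.0297 = 4.1. At p = 0.003: 0.0383 / 0.0090 = 4.3.
- 19 v 5, p = 0.01: 0.1738 / 0.0490 = 3.5. At p = 0.003: 0.0555 / 0.0149 = 3.7.
- 13 v 3, p = 0.01, drug doubles p: 0.5 × 0.1225 + 0.5 × (1 − 0.98^13) = 0.1767; 0.1767 / 0.0297 = 5.9. If the drug triples p: 0.2247 / 0.0297 = 7.6.

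**Simulation of the planned unadjusted Cox model.** Inputs from the documents: 1811 patients (SAP 2.3.1), 15% high risk (Protocol 15.1), 1:1 allocation within that stratum, follow-up of 104 to 230 weeks, Table 1 schedule. Assumed: no true CKD273 effect; drug RR 1, 2 or 3; either transient excursions (0.25 to 2% per test) or persistent hyperkalaemia (1 to 4% per year). There were 300 runs per setting. Values are median hazard ratios, high versus low risk.

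| Scenario | Drug RR 1 | Drug RR 2 | Drug RR 3 |
|---|---|---|---|
| Transient, as planned | 3.6–3.9 | 5.7–6.1 | 7.6–7.9 |
| Persistent, as planned | 0.95–1.04 | about 1.5 | about 2.0 |

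In the transient settings p < 0.05 occurred in 82 to 100% of runs. In the persistent settings it occurred in 2 to 4% with no drug effect, 30 to 72% at RR 2 and 65 to 100% at RR 3.

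**Which correction removes the bias (drug RR 3).**

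- Active arm removed, full schedule kept: still 3.8 to 4.0 if transient, about 1 if persistent.
- Annual visits only, active arm kept: 1.9 to 2.0 (transient).
- Both together: 0.88 to 1.01 across transient and persistent settings, with p < 0.05 in 2 to 5% of runs.

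Both corrections are needed, because the documents do not say which pattern of hyperkalaemia to expect.

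**Do other sections already correct K?** SAP 6.3.1.3 contains both ideas, moving events to annual visits and dropping the active arm, but each is stated for the primary endpoint. Its reason for dropping the active arm is that a beneficial drug would reduce endpoints; for K the drug would add them. Protocol 15.7 has secondary endpoints compared first between low-risk and high-risk placebo patients, and the Protocol synopsis adjusts them for study intervention. SAP 6.3.1.2 does neither.

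**The case against.** The strongest reply concerns size. Ratios of 4 to 8 need excursions that come and go independently between tests. If hyperkalaemia persists once present, yearly testing finds it too, and test frequency alone gives a hazard ratio of about 1. The documents give no event rate, within-patient correlation or drug effect that would decide between the two. This stands. A reader might infer that a large, significant CKD273 hazard ratio for K is practically certain; the documents do not support that.

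Second, there is mitigating text. SAP 6.4 plans models without the active arm, on all data and on annual samples, and names no endpoint, so it could be read to cover K. SAP 4.1 calculates secondary p-values only if the primary p-value is below 0.05, and rIDI needs a significant unadjusted hazard ratio. These soften the consequences. But SAP 6.4 is an additional analysis that would stand beside the biased model, and SAP 4.1 still provides confidence limits for all secondary analyses.

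Third, the safety question is properly answered elsewhere. SAP 6.3.2.2 includes K in the randomised Cox models and tests hyperkalaemia adverse events by arm. That is so, and it is why K can leave SAP 6.3.1.2 at little loss. The same exclusion list appears in both sections, which would fit a list copied from one to the other.

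Fourth, the active arm and unequal sampling also affect other high/low models, such as outcome D and the eGFR thresholds. That is fair; removing K does not settle those.

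Finally, a reader might note that K sets plasma and serum 0.3 mmol/L apart (5.5 and 5.8) while Protocol 7.2 sets them 0.4 apart ("Plasma potassium level >5.0 mmol/L or serum potassium level >5.4 mmol/L") and infer an error. The documents do not support this. An eligibility limit and an outcome threshold need not share an offset, and the true plasma–serum difference is not given.

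**Conclusion.** The concern holds as a matter of text and direction. As written, the SAP fits hyperkalaemia as a CKD273-predicted endpoint in a cohort where only high-risk patients can receive spironolactone and where they are tested about four times as often. The drug pushes the hazard ratio upwards if it raises potassium at all. Test frequency does so to the extent that excursions are transient, and otherwise leaves it near 1.

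The size is conditional on assumed rates and on no true CKD273 effect: about 3.5 to 4 from test frequency alone and up to about 8 with a drug RR of 3 if excursions are transient; about 1.5 to 2.0, from the drug only (RR 2 to 3), if hyperkalaemia is persistent. The primary analyses and the randomised safety comparison are unaffected.

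**What to change.** In SAP 6.3.1.2, change the list of excluded outcomes to C, H, J and K. Leave SAP 6.3.2.2 as it is, so that K is analysed as spironolactone versus placebo, where both arms share one visit schedule.

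If a high- versus low-risk figure for K is still wanted, compare low-risk with placebo-treated high-risk patients on annual-visit potassium only, descriptively and without rIDI. This also follows the order set in Protocol 15.7.

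The cost is one letter in the SAP and no new data. What is lost is the hazard ratio for K between all high-risk and low-risk patients, which could not be attributed to the score in any case.

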## 15.6 Analysis of primary endpoint

The primary endpoint is defined as time to the first occurrence of microalbuminuria (UACR >30 mg/g and <300 mg/g) in 2 out of 3 sterile first morning void urine samples with a geometric mean of UACR >30% above initial geometric mean UACR OR geometric mean > 40 mg/g in three samples. The baseline urinary albumin-to-creatinine ratios are the geometric mean of three measurements obtained during the "run-in" period.

It is expected, that the number of patients who will drop out between randomization and occurrence of microalbuminuria will be low (<15%).

If those cases where drop out occurs before sampling during the study period, prior to unblinding the treatment code it will be specified in the statistical analysis plan, whether these patients have to be considered as a treatment failure in the analysis of the primary endpoint.

The predictive value of a positive and negative test, specificity and sensitivity of the test in relation to prediction of development of the primary endpoint will be evaluated. To assess whether CKD273 classifier (the marker) improved risk prediction of the primary outcome we determined the concordance statistic (c-statistic) and Integrated Discrimination Improvement (IDI). Both parameters measure the discriminative ability of a marker in a model to distinguish between people who will or will not develop the outcome (in case of predictive methods).

The primary endpoint will be analyzed in the total population with comparisons of high- vs. low-risk pattern and active vs. placebo treatment using a Cox proportional-hazards regression model with treatment as a fixed effect; the baseline urinary albumin-to-creatinine ratio will be logarithmically transformed (base 10) as a covariate, and a two-tailed Wald chi-square test with an alpha level of less than 0.05; hazard ratios and two-sided 95 % confidence intervals will be calculated. Kaplan Meier plots of the groups will be made.

Secondly, the analyses will be adjusted for age, gender, center, HbA1c and BP. Thirdly, further adjustment for any baseline demographic variables which are significantly different between the groups and related to albuminuria at baseline will be calculated. In addition adjustment will be made for significant changes in RAAS blockade or treatment with aldosterone receptor antagonist as concomitant medication during the study period.

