## 15.7 Analysis of secondary endpoints

All secondary endpoints as described in section 5.5 will be analyzed to test if there is a difference in development of endpoints over time between a) active vs. placebo treated patients, and b) high-risk and low-risk population based on CKD273. As described in section 15.5.1 the analyses will initially compare low-risk with high-risk placebo treated patients, and secondly all high-risk patients. Adjustments will be performed as for the primary endpoint.

In addition to time to event (survival) analyses for discrete endpoints, analyses will evaluate the change over time in geometric mean UACR as slope analyses unadjusted as well as adjusted for confounders as described for the primary endpoint, comparing slope in the high-risk population with active vs. placebo and between low-risk and high-risk population the total population. Similar analyses will be performed with change in eGFR with time as the endpoint.

In the analyses with time to cardiovascular events, only time to first event in case of more than one event in a patient will be included.

In addition to the above described analyses comparing endpoints or slopes in high- vs. low-risk population or active vs. placebo, explorative analyses will also evaluate if the CKD 273 pattern and other baseline variables or changes in variables from baseline to 13 weeks visit in the high-risk population are predictive of development of endpoints.

Further analyses may be described in the SAP before database lock.

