2.3.3 Additional scientific objectives

To compare the rate of change in urinary albumin excretion rate in high vs. low-risk population (based on the proteomic test), and to compare the effect of spironolactone on rate of change in UACR in the intervention group.

In addition, the objective is to study the rate of change in eGFR in relation to urinary marker pattern (CKD 273) and the intervention with spironolactone.

To study the ability of urinary proteomic patterns, to predict cardiovascular or renal events during the study as well as response to intervention, in relation to study endpoints.

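### The high- versus low-risk slope models in SAP 6.3.1.2 drop most of the confounders the protocol promises and, on their ordinary reading, do not adjust the slope contrast

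*SAP*

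**What the plan says.** SAP 6.1.2 defines outcome C as "changes in geometric mean of UACR throughout the study period in all patients by assessing the slope of albuminuria changes", together with absolute change, and outcome H as "Change in eGFR (slope) from baseline and from three-month post-baseline to end of study". The related objective in SAP 2.3.3 is "To compare the rate of change in urinary albumin excretion rate in high vs. low-risk population".

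SAP 6.3.1.2 covers both outcomes in one sentence. It begins "To evaluate changes in UACR and eGFR over time (outcome measurement C and H in section 6.2.1" and ends "a linear mix model will be applied with adjustment for eGFR and UACR at baseline". (The cross-reference should be to 6.1.2; there is no section 6.2.1.) It does not state a risk-group-by-time term, covariate-by-time terms, random effects or the response scale. The fuller covariate list for the Cox models in the same section (age, gender, HbA1c, systolic blood pressure, retinopathy, eGFR, UACR) expressly leaves out outcomes C, H and J. SAP 6.3.2.2 uses the same slope sentence for spironolactone versus placebo.

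Protocol 15.7 plans "slope analyses unadjusted as well as adjusted for confounders as described for the primary endpoint". Its slope contrasts are spironolactone against placebo and the low- against the high-risk group, and eGFR is to be handled in the same way. Protocol 15.6 gives the confounders for the primary endpoint: "the baseline urinary albumin-to-creatinine ratio will be logarithmically transformed (base 10) as a covariate", then age, gender, center, HbA1c and blood pressure.

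**The concern.** High- and low-risk patients are separated by a urine test, not by randomisation. CKD273 was built from peptides associated with chronic kidney disease, and SAP 6.3.1.3 itself names higher age, HbA1c, systolic blood pressure and UACR, and lower eGFR, as known risk factors for overt kidney disease. Baseline differences between the risk groups that also bear on slope are therefore foreseeable, although the documents do not quantify them.

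The quantity of interest is a difference in slopes, which is the risk-group-by-time term. A covariate entered once, without a time interaction, explains differences in level. It does not explain why some patients decline faster. A slope difference could then be reported as adjusted for baseline eGFR and UACR when its value is essentially the unadjusted one, and age, gender, HbA1c and blood pressure would not have been considered at all.

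**Working it through.** The documents give no slope, SD or power for these analyses, so there is no planned figure to reproduce.

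**Step 1. Compare the covariate lists.**

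| Covariate | Protocol 15.6/15.7 (slopes) | SAP 6.3.1.2 Cox | SAP 6.3.1.2 slopes |
|---|---|---|---|
| Baseline UACR | yes, log10 | yes, scale not stated | yes, scale not stated |
| Baseline eGFR | no | yes | yes |
| Age, gender | yes | yes | no |
| HbA1c | yes | yes | no |
| Blood pressure | yes | yes (systolic) | no |
| Center | yes | no | no |
| Retinopathy | no | yes | no |

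Of the six protocol confounders, five are absent from the slope model. This gap is textual and holds however the model is coded. The unadjusted slope that the protocol promises is not named in the SAP either.

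**Step 2. What a main effect does to a slope contrast.** For patient *i* at time *t*, with risk group *G* and baseline covariate *X*:

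y = b0 + b1·G + b2·t + b3·G·t + g·X + d·X·t + random intercept + random slope·t + error

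The target is b3. If d·X·t is left out, the estimate of b3 converges to

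b3 + d × (mean X in high risk − mean X in low risk),

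exactly in balanced data and nearly so otherwise. The term g·X carries no time, so including it does not change this. The bias is zero if either factor is zero.

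**Step 3. Numerical check.** From the documents: N = 1811 (SAP 2.3.1), 15% high risk (Protocol 15.1), follow-up of 2 to 4.4 years, and visits every 13 weeks (high risk) versus annually (low risk). Assumed: baseline gap 0.5 SD; d = 0.10 per year per SD; no effect of CKD273 itself on slope (b3 = 0); covariate effect on level 0.6; SDs 0.3 (intercept), 0.08 (slope) and 0.35 (residual). There were eight simulated data sets per layout, with all models fitted to the same data.

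Expected bias: 0.5 × 0.10 = 0.05 per year.

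| Model | Balanced annual visits | 13-weekly vs annual |
|---|---|---|
| Mixed model, unadjusted | 0.0493 | 0.0497 |
| Mixed model, covariate as main effect | 0.0493 | 0.0504 |
| Mixed model, covariate × time | 0.0000 | 0.0008 |
| Per-patient slope regressed on group and covariate | 0.0000 | −0.0004 |

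The main effect changes nothing and the time interaction removes the bias. The last row matters: if each patient's slope is the response, a baseline main effect does adjust the contrast.

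**Step 4. Range.** The bias scales with the product of the two factors. In eGFR units, 0.3 SD × 0.3 ml/min/1.73m² per year per SD = 0.09 per year; 0.5 × 0.5 = 0.25 per year. These inputs are assumptions.

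**Step 5. Check the remedy.** Interacting an outcome's own observed baseline with time, while that baseline is also a response, can create bias: measurement error in the baseline raises the covariate and flattens or steepens the fitted slope together. With N = 1811, 15% high risk, residual SD 5, the trial's visit pattern, high-risk baseline eGFR 5 to 8 lower, and no true slope difference or confounding (100 replicates, per-patient slopes), rejection was 6% unadjusted. Adjusting for the observed baseline gave a spurious difference of −0.17 to −0.22 per year and 24% to 32% rejection. Removing the baseline value from the response brought rejection to 4%. The size depends on the assumed spread and error; the direction is the point.

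**The case against.** **The SAP never says main effects only.** A reader might infer that the SAP fixes a main-effects model and that the CKD273 slope result is therefore confounded. The text does not go that far. It is silent on interactions, and the last row of the Step 3 table shows a slope analysis in which baseline main effects do adjust. This stands. However, the SAP names a mixed model for change over time, and there covariates without time interactions are the ordinary meaning of adjustment. The missing protocol covariates do not depend on this question.

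**The objective is descriptive.** SAP 2.3.3 asks for a comparison of rates of change. If high-risk patients truly decline faster because their baseline UACR is higher, the unadjusted contrast answers that question correctly. This also stands, and it is why a reader should not attach a false-positive rate. Rates of 43% (inputs 0.5 and 0.5) and 10% (0.3 and 0.3) can be produced, but they rest on assumed inputs, come from regressions of per-patient slopes and not from the mixed model, and count as false only if the claim is an effect independent of UACR. What remains is the contrast that Protocol 15.7 wants adjusted.

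**UACR on the raw scale.** A reader might infer that UACR will be analysed untransformed. Outcome C is defined on the geometric mean and Protocol 15.6 uses log10 for the covariate, which points to the log scale. The geometric mean could refer only to averaging the three voids at a visit, so the scale needs stating, but no raw-scale analysis is established.

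**Limited reach.** Slopes are secondary, and SAP 4.1 gives secondary p-values only if the primary analysis is significant. Confidence limits are reported regardless. In SAP 6.3.2.2 randomisation protects the slope contrast, so the confounding point does not apply there.

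**Conclusion.** The point holds for the non-randomised CKD273 comparison. The SAP slope model omits age, gender, center, HbA1c and blood pressure, which the protocol promises for slopes. All but center are in the SAP's own Cox models in the same section, with blood pressure there as systolic. On its ordinary reading, the model also leaves the risk-group-by-time contrast essentially unadjusted even for the two covariates it names.

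The size is unknown. It equals the baseline gap times the covariate's effect on slope, and the documents give neither; 0.05 per year in Step 3 and 0.09 to 0.25 ml/min/1.73m² per year in Step 4 are illustrations. The documents do not support saying that the result will be confounded, that the SAP specifies a wrong model, or that UACR will be analysed raw. The log-scale item is a clarification. The change is worth making before analysis because it decides whether an adjusted slope difference can be read as adjusted.

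**What to change.** In SAP 6.3.1.2 only:

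- Write out the model: random intercept and slope, with fixed effects of risk group, time and risk group × time. Report the risk-group-by-time contrast unadjusted and adjusted, as Protocol 15.7 requires.
- For the adjusted contrast, add age, sex, HbA1c, systolic blood pressure and the other marker's baseline, each with a time interaction. The other marker is log-UACR in the eGFR model and eGFR in the UACR model.
- Reconcile center with Protocol 15.6: include it, or record why it is left out.
- Do not add the outcome's own observed baseline by time while baseline is also a response. Either keep baseline as a response only, or drop it from the response when it is a covariate.

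In SAP 6.3.1.2 and 6.3.2.2:

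- State that UACR is modelled on the log scale, with log-UACR wherever it is a covariate, and report percent change per year. With log10, this is 100 × (10^slope − 1).
- Correct the cross-reference from 6.2.1 to 6.1.2.

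No covariate-by-time terms are needed for confounding in 6.3.2.2.

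The cost is SAP wording, a few more model terms and a slightly wider interval for the adjusted slope. No new data are needed. Dropping baseline from the response loses one time point per patient, which weighs more in the low-risk group because it is seen annually.

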3.2 Randomization

At baseline eligible patients with a high-risk proteomics pattern will be included in the intervention part of the study. Randomization lists will be prepared by an independent statistician at the Robertson Centre, University of Glasgow, who is not involved into other tasks of the trial.

The patients will be randomly assigned in a 1:1 ratio to one of the two treatment arms using a block randomization stratified by study center.

Patients will be stratified in the two treatment arms (1:1) based on whether or not the patients is treated with RAS blocking agents at the time of entry (Screening) in order to have the number on RAS blocking agents balanced in the two treatment arms.

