6.3.1.3 Sensitivity analysis

In order to out-balance the fact that the "high"-risk stratum has primary outcome measures every third month we will perform a sensitivity analysis on the primary endpoint. Any primary endpoint in the "high"-risk stratum between annual visits will be carried forward to the date of the following annual visit. This analysis is most likely underpowered because of exclusion of endpoints in the high-risk stratum, however, the trend of the primary analysis is expected.

As in the "high"-risk group we have participants allocated to either active IMP or placebo we potentially limit the number of endpoints if the active IMP is beneficial. To adjust for this potential effect, we will perform a sensitivity analysis on the primary endpoint only in "low"-risk participants and in "high"-risk participants allocated to placebo treatment. This analysis is most likely also underpowered because of exclusion of endpoints in the "high"-risk stratum, however the trend of the primary analysis is expected.

ANOVA models for each continuous variable measured at baseline: age, HbA_{1c}, systolic blood pressure, Study site, eGFR and UACR will be tested within each stratum "high"- and "low"-risk as well as interaction in the Cox-model between strata with the primary endpoint as determinant. Chi square tests will be used for categorical variables: gender, use of antihypertensive agents, known cardiovascular disease and retinopathy.

We expect a correlation between the “high”-risk stratum and events of the primary endpoint for participants with known risk factors for overt kidney disease (higher age, HbA_{1c}, systolic blood pressure, UACR, and lower eGFR, male gender, use of antihypertensive agents, known cardiovascular disease and retinopathy).

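### The high- versus low-risk comparison of UACR and eGFR change (SAP outcomes C and H) pools spironolactone and placebo patients with no treatment term, so it carries about half of any drug effect; Protocol 15.7 puts a placebo-only comparison first

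*SAP*

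**What the plan says.** SAP 6.3.1 is run in the observational cohort, defined in SAP 4.3.2 as "All participants with valid proteomic score and data at baseline visit". That definition takes in both randomised arms. SAP 3.2 gives the allocation within the high-risk group: "The patients will be randomly assigned in a 1:1 ratio to one of the two treatment arms".

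Outcome C (SAP 6.1.2) covers UACR by "assessing the slope of albuminuria changes and absolute changes from inclusion to end of trial". Outcome H is the eGFR slope, both from baseline and from three months after baseline. For both outcomes SAP 6.3.1.2 states that "a linear mix model will be applied with adjustment for eGFR and UACR at baseline". It names no other covariate, no treatment term and no restriction to placebo.

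Protocol 15.7 opens with "All secondary endpoints as described in section 5.5 will be analyzed" and then sets an order for the risk-group comparison: "the analyses will initially compare low-risk with high-risk placebo treated patients, and secondly all high-risk patients". Protocol 5.5.1 lists both the albuminuria change and the eGFR change among those endpoints.

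The SAP removes the active arm in two other places. In 6.3.1.3, "we will perform a sensitivity analysis on the primary endpoint only in" low-risk patients and placebo-allocated high-risk patients. In 6.4, an analysis without the active arm is planned, but for Cox models only. SAP 6.3.1.2 leaves C and H out of its secondary-endpoint Cox models.

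**The concern.** SAP 2.3.3 makes it an objective to compare the rate of change in albumin excretion between risk groups and to relate eGFR change to the CKD273 pattern. A risk-group contrast in which half of one group is allocated to an albumin-lowering drug does not answer that question cleanly. SAP 6.3.1.3 recognises that active drug may reduce endpoints in the high-risk group, but its remedy does not extend to C and H.

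For UACR the main risk is that a true faster rise in high-risk patients is diluted, or appears as a fall relative to low-risk patients. For eGFR, an early drop on drug would steepen the pooled slope from baseline.

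**Working it through.** 1. **The plan's own figure.** The documents give no power, sample size or effect size for C or H. The only sample-size figure is 129 per arm for 40% versus 24%. With two-sided alpha 0.05, power 0.80 and unpooled variance: n = (1.960 + 0.842)² × (0.40×0.60 + 0.24×0.76) / 0.16² = 129.5. The figure is reproduced, but it does not bear on this point.

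2. **What the pooled contrast estimates.** With 1:1 allocation, pooled high-risk mean = placebo mean + 0.5 × drug effect. Subtracting the low-risk mean gives: pooled contrast = CKD273 contrast + 0.5 × drug effect. Half is by allocation; exposure may be lower after discontinuation.

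3. **Size for UACR on the log scale.** SAP 2.1 cites a 20-30% reduction in albumin excretion, in proteinuric patients. Applying it to normoalbuminuric patients is an assumption.
   - 20% lowering: 0.5 × ln(0.80) = −0.112, so the ratio is multiplied by exp(−0.112) = 0.894. A true high/low ratio of 1/0.894 = 1.12 would appear as 1.00.
   - 30% lowering: 0.5 × ln(0.70) = −0.178, multiplier 0.837. A true ratio of 1/0.837 = 1.20 would appear as 1.00.

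4. **Simulation with no CKD273 effect, UACR.** Setting: 1539 low-risk and 272 high-risk patients (15% of the SAP's 1811), 136 of them on drug. Follow-up is 2 to 4.4 years, with visits every 13 weeks in high-risk and yearly in low-risk patients, plus end of study. Assumed: within-visit SD of log UACR 0.35, slope SD 0.10 per year, immediate lowering on drug. Slopes are precision-weighted per-patient slopes, approximating the mixed model. Absolute change uses a Welch test, because the SAP names none. Ranges span repeated runs of 150 to 400 trials per setting; Monte Carlo error is up to about 4 points. Entries are the share of trials rejecting at 0.05.

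| Assumed lowering | Pooled slope from baseline | Pooled absolute change |
|---|---|---|
| 5% | about 5% | 9-10% |
| 10% | about 5% | 24-27% |
| 20% | 30-33% | 80-84% |
| 30% | 56-59% | 99-100% |

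   The absolute-change rejections are almost all in the direction opposite to the hypothesis. The placebo-only comparison stays near 5%.

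5. **Simulation with a true extra rise of 5% per year in high-risk patients.** For absolute change, power is 82-86% placebo-only, against 19-21% pooled at 20% lowering and 5-9% at 30%. For the slope, pooled power falls only to 88-96%. Masking is therefore mainly a problem for absolute change.

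6. **eGFR.** The documents give no drug effect on eGFR. Assuming residual SD 5, slope SD 2, an early drop of 3 to 5 ml/min and no CKD273 effect, the pooled slope from baseline rejects in 19-23% of trials (drop of 3) and 37-49% (drop of 5). The slope from three months rejects in 3-7%.

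7. **Precision cost of placebo-only.** With the planned 300 high-risk and 1700 low-risk patients: √[(1/150 + 1/1700) / (1/300 + 1/1700)] = √1.85 = 1.36.

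**The case against.** **The Protocol is not unambiguous for slopes.** A later paragraph of 15.7 describes the slope analyses as "comparing slope in the high-risk population with active vs. placebo and between low-risk and high-risk population the total population" and does not repeat the placebo-first order; the order itself is tied to a Section 15.5.1 that does not exist. A reader might infer either that the SAP plainly breaches the Protocol or that the Protocol intended pooling. Neither is secure. The placebo-first sentence covers every Section 5.5 endpoint and is not withdrawn, and the total-population wording fits its second step.

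**The SAP does not write out the mixed model.** That is so. Pooling follows from the cohort definition, and from the SAP saying explicitly elsewhere when the active arm is excluded.

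**P-values are gated.** SAP 4.1 gives secondary p-values only if the primary analysis has p<0.05. If that means the high- versus low-risk primary analysis, a two-proportion approximation (8.5% event rate in both groups, drug reducing events by 0-40%, all assumed) opens the gate in only about 5-14% of trials when CKD273 has no effect. False-positive p-values would then seldom be reported. This stands, but SAP 4.1 provides confidence limits regardless, and masking matters most when CKD273 does predict, which is when the gate is likely to be open.

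**The SAP also fits C and H by treatment arm (6.3.2.2).** That would alert a reader to a drug effect, but does not remove it from the risk-group contrast.

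**The large figures depend on strong assumptions.** Agreed: the slope is materially affected only at 20-30% lowering, and the largest rejection rates belong to a test of absolute change that the SAP does not specify.

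**Conclusion.** The point holds for a secondary analysis and should be corrected. As planned, the risk-group contrast for C and H contains about half of any drug effect, and no planned analysis gives a version free of it. For UACR the expected harm is dilution or reversal of a true high-risk excess: a multiplier of 0.89 to 0.84 at 20-30% lowering, with the pooled slope rejecting in about 30-60% of trials when CKD273 has no effect. At 5-10% lowering the slope is at or only slightly above nominal. Absolute change is affected more. These rates rest on assumed SDs and an immediate drug effect.

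Two stronger readings are not supported. One is that an effective drug would create false support for CKD273. For UACR the bias runs against the hypothesis. For eGFR it would need an early drop whose size the documents do not give, and it would reach only the slope from baseline, since the three-month slope in outcome H is largely protected. The other is that a formal null hypothesis on rate of change is being tested wrongly: SAP 2.3.3 states objectives only, and the documents' stated nulls concern development of the microalbuminuria endpoint.

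**What to change.** In SAP 6.3.1.2, make low-risk versus high-risk placebo the first mixed model for outcome C (slope and absolute change) and outcome H (both slopes). Absolute change should be requested for C only, because outcome H in the SAP is slope only. Give all high-risk patients second, with treatment and treatment-by-time terms, so that the risk-group contrast refers to untreated patients. In the same edit, write out the risk-group and time terms, state how absolute change in C will be tested, and correct the reference to Section 6.2.1 (the outcomes are in 6.1.2).

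The cost is SAP wording, one extra model, and a placebo-only standard error about 1.36 times that of the pooled contrast. No new data are needed.
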